15.1 Adverse Events

An AE is defined as any untoward medical occurrence associated with the use of a drug in humans, whether or not considered drug-related. An AE can therefore be any unfavorable and unintended sign (eg, an abnormal laboratory finding), symptom, or disease occurring after the subject started dosing with the study drug, without any judgment about causality. Any pre-existing medical condition that worsens after administration of the study drug will also be considered a new AE. Study drug includes the investigational drug under evaluation and placebo. All AEs will be coded using MedDRA Version 20.1.

Treatment-emergent adverse events (TEAEs) are defined as any AE that occurs or worsens after the first dose of study treatment. AEs recorded in the eCRF which began prior to treatment will not be included in the summary tables but will be included in the AE data listings.

An overall summary will be presented that includes the number of AEs, TEAEs, serious AEs (SAE), and serious TEAEs (TE-SAE). The summary will also include the number and percentage of subjects withdrawn due to an AE, the number and percentage of subjects with an AE resulting in death, and the number and percentage of subjects who experienced at least one AE, TEAE, SAE and TE-SAE, by treatment group and for all subjects. This summary will include breakdowns of AEs further categorized as ocular or non-ocular.

Additional summaries of TEAEs will be provided showing the number and percentage of subjects who experienced at least one TEAE. These summaries will be presented by SOC and PT. Non-ocular TEAEs will be summarized using discrete summary statistics and presented by treatment group at the subject and event level by SOC and PT. Ocular TEAEs will be similarly summarized at the subject and event level as well as for study and fellow eyes separately. If a subject reports the same PT multiple times within the same SOC, that PT will only be reported once within that SOC. As with the PT, if a subject reports multiple conditions within the same SOC, that SOC will only be reported once. In the summary, SOC will be listed in order of descending frequency for all subjects; PTs will be listed in order of descending frequency for all subjects within each SOC. The occurrence of non-ocular and ocular TEAEs will also be tabulated by SOC, PT, and maximal severity.

The relationship of each adverse event to the investigational product should be determined by the Investigator (in a blinded manner) using these explanations:

- *Definite*: When there are good reason and sufficient documentation to demonstrate a direct causal relationship between investigational product and AE.
- *Probable*: When there are good reasons and sufficient documentation to assume a causal relationship in the sense of plausible, conceivable, likely but not necessarily highly probable.
- *Possible*: When there is sufficient information to accept the possibility of a causal relationship in the sense of not impossible and not unlikely, although the connection is uncertain or doubtful, for example; due to missing data or insufficient evidence.
- *None*: When there is sufficient information to accept a lack of a causal relationship, in the sense of impossible and improbable.
- *Unclassified*: When the causal relationship is not assessable for whatever reason due to insufficient evidence, conflicting data or poor documentation.

All possible, probable, and definite TEAEs are considered as treatment-related TEAEs.

Separate summaries will be provided for the following categories of AEs:

- Ocular TEAEs
- Non-ocular TEAEs
- Treatment-related ocular TEAEs
- Treatment-related non-ocular TEAEs
- SAEs

Severity of an adverse event is defined as a qualitative assessment of the degree of intensity of an adverse event as determined by the Investigator or reported to him/her by the patient/subject. The assessment of severity is made irrespective of relationship to study drug or seriousness of the event and should be evaluated according to the following scale:

- *Mild*: Event is noticeable to the subject, but is easily tolerated and does not interfere with the subject's daily activities.
- *Moderate*: Event is bothersome, possibly requiring additional therapy, and may interfere with the subject's daily activities.
- *Severe*: Event is intolerable, necessitates additional therapy or alteration of therapy, and interferes with the subject's daily activities.

Summaries of TEAEs by maximal severity will be presented for ocular AEs and non-ocular AEs separately. The number of subjects with any TEAEs (along with percentages) will be tabulated by SOC and PT within each SOC by treatment group. To count the number of subjects with any TEAEs, if a subject has multiple TEAEs coded to the same PT within the same SOC, the subject will be counted once under the maximal severity.

All AEs will be presented in a subject listing that classifies each AE as ocular or non-ocular and indicates whether it is a TEAE. Separate listings will be produced for AEs leading to study discontinuation, AEs leading to death and SAEs.

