The change in EDS from pre- to post-treatment will be analyzed using an ANCOVA model with pre-treatment EDS as a covariate and with treatment and time point as fixed effects (accounting for repeated measures). LS means for each treatment, the corresponding 95% CIs, and the estimated treatment difference between each dose of OC-02 Nasal Spray and placebo will be calculated from this ANCOVA model. A study site by treatment interaction will also be explored in a separate model to evaluate how the treatment effect may differ across study sites.

The primary analyses will be performed on the ITT population on observed data. Two-sample t-tests and non-parametric Wilcoxon rank sum tests will be used to compare treatments as unadjusted sensitivity analyses. Sensitivity analyses will also be performed on the ITT population with multiple imputation (MI) to impute missing data, as well as the PP population with observed data only.

Other Efficacy Analyses:

Change from pre to post-treatment in EDS will also be analyzed at each individual time point in a manner similar to the primary analysis for Schirmer's Test. These ANCOVA models will include pre-treatment EDS, treatment and study site as covariates.

Change from pre-to post-treatment in [REDACTED] Ocular Discomfort Scale results will be summarized by visit, time point (where appropriate) and treatment with quantitative descriptive statistics and will be analyzed at each individual time point in a manner similar to EDS.

The analyses will be performed for observed data only for the ITT and PP populations.

Safety Variables:

AEs will be coded using the Medical Dictionary for Regulatory Activities (MedDRA) dictionary. Frequencies and percentages of subjects with treatment-emergent AEs (TEAEs), serious TEAEs, and TEAEs causing premature discontinuation will be provided by treatment group. An AE is treatment emergent if it occurs or worsens after the first dose of study treatment. Furthermore, frequencies will be given of subjects with TEAEs by system organ class, by system organ class and preferred term, by system organ class, preferred term and maximal severity, by system organ class, preferred term and strongest relationship, and by system organ class, preferred term, maximal severity, and strongest relationship. Separate analyses will be performed for ocular specific and all AEs (including systemic).

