10.3 Sample Size

The sample size for this study is not based on statistical power considerations. It is expected that approximately 40 subjects will be enrolled in each of the four treatment arms, for a total of approximately 160 randomized subjects. Assuming a 5% drop out rate, approximately 38 subjects per group are expected to complete the study.

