This SAP describes the data that will be analyzed and the subject characteristics, efficacy, and safety assessments that will be evaluated. This SAP provides details of the specific statistical methods that will be used. The statistical analysis methods presented in this document will supersede the statistical analysis methods described in the clinical protocol. If additional analyses are required to supplement the planned analyses described in this SAP they may be completed and will be identified in the CSR.

2. Study Objectives

The objective of this study is to evaluate the safety and effectiveness of OC-02 Nasal Spray as compared to placebo on signs and symptoms of dry eye disease (DED).

3. Study Variables

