[figure not shown]
Table Number	Title	Population
TABLE 14.2.1.15	SCHIRMER'S TEST IN FELLOW EYE, BASELINE EYE DRYNESS SCORE < 60	ITT WITH ODO
TABLE 14.2.1.16	SCHIRMER'S TEST IN FELLOW EYE, BASELINE EYE DRYNESS SCORE >= 60	ITT WITH ODO
TABLE 14.2.2.1	EYE DRYNESS SCORE ONE-TIMEPOINT ANALYSIS	ITT WITH ODO
TABLE 14.2.2.2	EYE DRYNESS SCORE ONE-TIMEPOINT ANALYSIS	ITT WITH MCMC
TABLE 14.2.2.3	EYE DRYNESS SCORE ONE-TIMEPOINT ANALYSIS	PP WITH ODO
TABLE 14.2.2.4	EYE DRYNESS SCORE ONE-TIMEPOINT ANALYSIS BY SITE	ITT WITH ODO
TABLE 14.2.2.5	EYE DRYNESS SCORE ONE-TIMEPOINT ANALYSIS TIPPING POINT ANALYSIS	ITT WITH MCMC
TABLE 14.2.2.6	EYE DRYNESS SCORE ONE-TIMEPOINT ANALYSIS	ITT WITH PMM
TABLE 14.2.3.1	EYE DRYNESS SCORE DURING CAE BY TIMEPOINT	ITT WITH ODO
TABLE 14.2.3.2	EYE DRYNESS SCORE DURING CAE BY TIMEPOINT	PP WITH ODO
TABLE 14.2.3.3	EYE DRYNESS SCORE POST-TREATMENT THREE-TIMEPOINT ANALYSIS	ITT WITH ODO
TABLE 14.2.3.4	EYE DRYNESS SCORE POST-TREATMENT THREE-TIMEPOINT ANALYSIS	PP WITH ODO
TABLE 14.2.3.5	EYE DRYNESS SCORE DURING CAE MMRM ANALYSIS	ITT WITH ODO
TABLE 14.2.3.6	EYE DRYNESS SCORE DURING CAE MMRM ANALYSIS	PP WITH ODO
TABLE 14.2.3.7	OCULAR DISCOMFORT ([REDACTED] SCALE) DURING CAE BY TIMEPOINT	ITT WITH ODO
TABLE 14.2.3.8	OCULAR DISCOMFORT ([REDACTED] SCALE) DURING CAE BY TIMEPOINT	PP WITH ODO
TABLE 14.3.1.1	ADVERSE EVENT SUMMARY	SAFETY
TABLE 14.3.1.2	ALL OCULAR ADVERSE EVENTS	SAFETY
TABLE 14.3.1.3	ALL NON-OCULAR ADVERSE EVENTS	SAFETY

Table Number	Title	Population
TABLE 14.3.1.4	ALL OCULAR TREATMENT-EMERGENT ADVERSE EVENTS	SAFETY
TABLE 14.3.1.5	ALL NON-OCULAR TREATMENT-EMERGENT ADVERSE EVENTS	SAFETY
TABLE 14.3.1.6	ALL OCULAR TREATMENT-RELATED TREATMENT-EMERGENT ADVERSE EVENTS	SAFETY
TABLE 14.3.1.7	ALL NON-OCULAR TREATMENT-RELATED TREATMENT-EMERGENT ADVERSE EVENTS	SAFETY
TABLE 14.3.1.8	ALL SERIOUS ADVERSE EVENTS	SAFETY
TABLE 14.3.1.9	ALL SERIOUS TREATMENT-RELATED TREATMENT-EMERGENT ADVERSE EVENTS	SAFETY
TABLE 14.3.1.10	ALL OCULAR TREATMENT-EMERGENT ADVERSE EVENTS BY MAXIMAL SEVERITY	SAFETY
TABLE 14.3.1.11	ALL NON-OCULAR TREATMENT-EMERGENT ADVERSE EVENTS BY MAXIMAL SEVERITY	SAFETY
TABLE 14.3.2	BEST-CORRECTED VISUAL ACUITY - LOGMAR	SAFETY
TABLE 14.3.3.1	SLIT LAMP BIOMICROSCOPY	SAFETY
TABLE 14.3.3.2	SHIFT IN SLIT LAMP BIOMICROSCOPY	SAFETY
TABLE 14.3.4.1	INTRANASAL EXAMINATION	SAFETY
TABLE 14.3.4.2	SHIFT IN INTRANASAL EXAMINATION	SAFETY
TABLE 14.3.5	PUPIL DIAMETER (MM)	SAFETY
TABLE 14.3.6	EXPOSURE TO STUDY DRUG	SAFETY

21. Listings

Listing Number	Title

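### TEAEs with Unclassified causality are left out of the treatment-related tables, in the same way as events rated None

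*SAP*

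**What the plan says.** SAP 15.1 lists five levels for the relationship of an adverse event to study drug: Definite, Probable, Possible, None and Unclassified. Protocol 9.1.2 has the same scale and does not say how the levels are grouped for analysis. Three definitions matter here:

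- The Unclassified level applies as follows: "When the causal relationship is not assessable for whatever reason due to insufficient evidence, conflicting data or poor documentation".
- The None level has a different basis: "When there is sufficient information to accept a lack of a causal relationship, in the sense of impossible and improbable".
- Possible includes events "although the connection is uncertain or doubtful, for example; due to missing data or insufficient evidence".

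The SAP then sets the analysis rule: "All possible, probable, and definite TEAEs are considered as treatment-related TEAEs". According to the table list in SAP section 20, three outputs use it: Table 14.3.1.6 ("ALL OCULAR TREATMENT-RELATED TREATMENT-EMERGENT ADVERSE EVENTS"), Table 14.3.1.7 (the non-ocular counterpart) and Table 14.3.1.9 (serious treatment-related TEAEs).

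The protocol synopsis planned TEAE frequencies "by system organ class, preferred term and strongest relationship". No table title in the SAP list corresponds to that. The SAP introduction says: "The statistical analysis methods presented in this document will supersede the statistical analysis methods described in the clinical protocol".

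**The concern.** The scale separates two situations: enough information to accept that the drug was not responsible, and too little information to judge. The grouping rule treats them alike, because neither enters a treatment-related table. No readable section gives Unclassified events a default, a row of their own or a sensitivity count.

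The boundary with Possible adds to the problem. Insufficient evidence appears in the definitions of both Possible and Unclassified, but Possible counts as related and Unclassified does not. Two investigators with the same thin record could choose differently. With up to three sites (Protocol 5.1), part of the related-event count could reflect rating habit.

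At stake is how the treatment-related tables are read in a trial that compares three doses with placebo and has safety in its objective. The efficacy analyses are not affected.

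**Working it through.** The plan states no figure that depends on this rule, so there is none to reproduce. The check sets the categories against the rule and then gives a sense of scale.

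**1. Categories against the rule (SAP 15.1)**

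| Category | Basis | In the treatment-related tables? |
|---|---|---|
| Definite | direct causal link documented | yes |
| Probable | causal link plausible | yes |
| Possible | link uncertain, including thin evidence | yes |
| None | enough information to accept no link | no |
| Unclassified | link cannot be assessed | no |

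Three of the five categories are counted. The last two rows have different bases and the same treatment.

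**2. Where an Unclassified TEAE still appears (SAP 15.1 and sections 20 and 21)**

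- all-TEAE tables 14.3.1.4 and 14.3.1.5: yes
- severity tables 14.3.1.10 and 14.3.1.11: yes
- SAE table 14.3.1.8, if serious: yes
- Listing 16.2.7.1 of all adverse events: yes
- treatment-related tables 14.3.1.6, 14.3.1.7 and 14.3.1.9: no

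**3. Size per affected subject**

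Input: about 40 subjects per arm (Protocol 10.3: "It is expected that approximately 40 subjects will be enrolled in each of the four treatment arms"). One subject whose only candidate event is Unclassified changes the arm's rate by 1/40 = 2.5 percentage points. The starting counts below are illustrations, since the documents give none. Formula: (related + Unclassified-only) / 40.

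| Related subjects | +0 | +1 | +2 | +4 |
|---|---|---|---|---|
| 4 | 10.0% | 12.5% | 15.0% | 20.0% |
| 8 | 20.0% | 22.5% | 25.0% | 30.0% |

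**4. Chance that any subject is affected**

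Let q be the proportion of subjects whose only candidate event is Unclassified. The documents give no value, so q is an assumption shown over a range. P(at least one) = 1 − (1 − q)^n.

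| q (assumed) | one arm, n = 40 | whole trial, n = 160 |
|---|---|---|
| 0.5% | 18% | 55% |
| 1% | 33% | 80% |
| 2% | 55% | 96% |
| 5% | 87% | nearly 100% |

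These are chances that the tables would change at all. They say nothing about whether the events were caused by the drug. If q is zero, nothing changes.

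**5. Effect on the contrast with placebo**

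Suppose an active arm has 8 related subjects, placebo has 4, and each arm has one further Unclassified-only subject. The rates go from 20.0% and 10.0% to 22.5% and 12.5%. The difference stays at 10.0 points, while the ratio falls from 20.0/10.0 = 2.0 to 22.5/12.5 = 1.8. Counting Unclassified events as related therefore raises the counts but need not widen the contrast.

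**The case against.** The strongest reply has five parts.

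- **No label of unrelated.** A reader might infer that the SAP counts Unclassified events as not treatment-related. It does not say so: it defines no unrelated group and lists no such table. The events are absent from one subset because the list of counted categories omits them. This stands, and the point is limited to that omission.
- **Nothing disappears.** All-TEAE rates by arm support the randomized, masked comparison with placebo without any causality judgment. This also stands. It confines the point to three tables but does not justify the grouping inside them.
- **Possible already takes in some poorly documented events.** True, and that reduces the number affected. The same overlap makes the split between Possible and Unclassified depend on the rater.
- **Understatement is not shown.** A reader might infer that the rule does understate drug-related events, or that it distorts a main safety output. The documents support neither. No Unclassified rate is given. The overall AE summary in SAP 15.1 has no related-event line, and the synopsis leads with TEAEs, serious TEAEs and TEAEs causing discontinuation. Causality is judged masked, so Unclassified events can arise on placebo too.
- **Redaction.** SAP 9.2, on missing or inconclusive data, and Protocol 10.4.7, on safety variables, cannot be read, so a supplementary rule there cannot be excluded. Against that, Unclassified is an assigned category and not a missing value, and the readable rule in SAP 15.1 is explicit.

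One could add that counting Unclassified as related merely merges it with a different neighbour. That holds if the merged count stands alone; showing the Unclassified number beside it keeps the distinction.

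The by-relationship tabulation in the synopsis could have shown Unclassified separately. Its absence from the SAP table list, without mention in SAP section 18, is a separate matter and the point does not rest on it.

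**Conclusion.** The point holds in a limited form. On the readable text, a TEAE with unassessable causality is left out of Tables 14.3.1.6, 14.3.1.7 and 14.3.1.9 exactly as an event rated None is, although the scale sets a different evidential requirement for each. No listed table is described as showing the Unclassified events separately.

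The effect is about 2.5 percentage points of an arm's related-event rate for each affected subject, assuming 40 per arm. The related count is understated only if such events occur and some are drug-related, and the documents do not allow either to be estimated. The conclusion also assumes that the redacted sections contain no further rule. This is a cheap improvement to a descriptive safety summary.

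**What to change.** In SAP 15.1, extend the definition so that, for Tables 14.3.1.6, 14.3.1.7 and 14.3.1.9, TEAEs rated Unclassified count as treatment-related together with Possible, Probable and Definite. In each of the three tables, add a row or footnote with the number of Unclassified events per arm, so that the count can be read with and without them. If a redacted section already has a rule for inconclusive causality, refer to it in SAP 15.1 and make the two agree.

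The cost is one SAP sentence and one extra row or footnote in three tables, settled before unmasking. No new data are needed. The downside is a slightly higher related-event count, possibly in the placebo arm too.

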15.2 Best-Corrected Visual Acuity (BCVA)

The visual acuity procedure will be performed at pre- and post-treatment at Visit 1 and may be performed post-CAE® at Visit 2 at the Investigator's discretion as needed. The logarithm of the minimum angle of resolution (logMAR) VA must be assessed using an ETDRS chart. The procedure used will be consistent with the recommendations provided for using the ETDRS eye chart. Subjects should use their most recent correction to attain their corrected distance visual acuity (CDVA).

The observed and change from baseline visual acuity will be summarized for each eye (study eye and fellow eye) using continuous descriptive statistics by visit for each treatment group. A subject listing of visual acuity will also be produced. This listing will also include values used in the calculation of BCVA including base logMAR, which is the last line in which a letter is read correctly, N, which is the number of letters missed up to and including the last line read, and T, which is a multiplier equal to 0.02.

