Other safety endpoints including visual acuity, slit-lamp biomicroscopy and intranasal endoscopic examination will be summarized by treatment group and visit using descriptive statistics. Changes or shifts from baseline will also be summarized where appropriate. For assessments performed by eye, study eye and fellow eye will be summarized separately. In addition, shifts from baseline to worst on-treatment value for ocular safety assessments will be summarized.

Summary of Known and Potential Risks and Benefits to Human Subjects

There are no known risks with the instillation of OC-02 Nasal Spray.

TABLE OF CONTENTS

Synopsis	3
Table of Contents	10
List of Abbreviations	13
1 Introduction	14
2 Study Objectives	15
3 Clinical Hypotheses	15
4 Overall Study Design	15
5 Study Population	17
5.1 Number of Subjects	17
5.2 Study Population Characteristics	17
5.3 Inclusion Criteria	17
5.4 Exclusion Criteria	18
5.5 Withdrawal Criteria	20
6 Study Parameters	20
6.1 Efficacy Measures	20
6.1.1 Primary Efficacy Measures	20
6.2 Safety Measure	20
6.3 Other Measures	20
7 Study Materials	20
7.1 Study Drug(s)	20
7.1.1 Formulations	20
7.1.2 Dispensation Schedule	20
7.1.3 Instructions for Use.....	21
7.2 Other Study Supplies	26
8 Study Methods and Procedures	26
8.1 Participant Entry Procedures	26
8.1.1 Overview	26
8.1.2 Informed Consent.....	26
8.1.3 Washout Intervals	27
8.1.4 Procedures for Final Study Entry.....	27
8.1.5 Methods for Assignment to Treatment Groups	27
8.2 Concurrent Therapies	27
8.2.1 Prohibited Medications/Treatments	27
8.2.2 Escape Medications	27
8.2.3 Special Diet or Activities	27
8.3 Examination Procedures	28
8.3.1 Procedures to be Performed at Each Study Visit with Regard to Study Objectives(s).....	28
8.4 Schedule of Visits, Measurements and Dosing	30
8.4.1 Scheduled Visits.....	30

8.4.2	Unscheduled Visits	30
8.5	Compliance with Protocol.....	30
8.6	Subject Disposition	30
8.6.1	Completed Subjects	30
8.6.2	Discontinued Subjects.....	30
8.7	Study Termination	31
8.8	Study Duration	31
8.9	Monitoring and Quality Assurance	31
9	Adverse Events	31
9.1	Adverse Event	31
9.1.1	Severity	32
9.1.2	Relationship to Study Drug.....	32
9.1.3	Expectedness.....	32
9.2	Serious Adverse Events.....	33
9.3	Procedures for Reporting Adverse Events.....	34
9.3.1	Reporting a Suspected Unexpected Adverse Reaction	34
9.3.2	Reporting a Serious Adverse Event	34
9.4	Procedures for Unmasking of Study Drug.....	35
9.5	Type and Duration of the Follow-up of Subjects after Adverse Events..	35

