4 OVERALL STUDY DESIGN

This is a Phase 2, multicenter, randomized, double-masked, placebo-controlled study designed to evaluate the safety and efficacy of OC-02 nasal spray in adult participants with DED. Approximately 160 subjects at least 22 years of age with a subject-reported history of dry eye and meeting all other study eligibility criteria will be randomized to receive an application of OC-02 or placebo at Visit 1 and Visit 2.

Participants who terminate early during the application period will be asked to complete safety assessments (if the participants agree) prior to study exit. Participants who are terminated early from the study will not be replaced.

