8.4.2 Unscheduled Visits

These visits may be performed in order to ensure subject safety. All procedures performed at an unscheduled visit will be recorded in the source documents and on the Unscheduled Visit eCRF pages. Any procedure indicated in the eCRF that is not performed should be indicated as “Not done.”

Evaluations that may be conducted at an Unscheduled Visit include:

- Slit-lamp Biomicroscopy;
- Visual Acuity;
- Intranasal Examination;
- Urine Pregnancy Test (if applicable);
- Assessment of AEs;
- Assessment of concurrent medications and/or treatments; and
- Any other assessments needed in the judgment of the investigator.

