A maximum effort should be made to identify each letter on the chart. When the participant says s/he cannot read a letter, s/he should be encouraged to guess. If the participant identifies a letter as one of two letters, s/he should be asked to choose one letter and, if necessary, to guess. When it becomes evident that no further meaningful readings can be made, despite encouragement to read or guess, the examiner should stop the test for that eye. However, all

letters on the last line should be attempted as letter difficulties vary and the last may be the only one read correctly. The number of letters missed or read incorrectly should be noted.

LogMAR Visual Acuity Calculations

The last line in which a letter is read correctly will be taken as the base logMAR reading. To this value will be added the number "N x 0.02" where 'N' represents the total number of letters missed up to and including the last line read. This total sum represents the logMAR visual acuity for that eye.

Example: Participant correctly reads 4 of 5 letters on the 0.2 line, and 2 of 5 letters on the 0.1 line.

Base logMAR	= 0.1
N (total number of letters incorrect on line 0.2 as well as 0.1)	= 4
N x T (T=0.02)	= 0.08
Base logMAR + (N x T)	= 0.1 + 0.08
logMAR visual acuity	= 0.18

Repeat the procedure for the left eye.

In order to provide standardized and well-controlled assessments of visual acuity during the study, all visual acuity assessments at a single site must be consistently done using the same lighting conditions and same correction if possible during the entire study. If the same correction cannot be used (i.e., a participant broke his/her glasses), the reason for the change in correction should be documented.

Note: A clinically significant visual acuity decrease (defined as an increase of 0.22 or greater in logMAR score) from the Screening Visit (Visit 1) should be evaluated by the Investigator as a potential AE.

Slit Lamp Biomicroscopy

Slit lamp biomicroscopy will be performed during the study. Observations will be graded as *Normal* or *Abnormal*. Abnormal findings, which are clinically significant, will be described. The following will be examined at each visit:

- Cornea
- Conjunctiva
- Anterior Chamber
- Lid

Corneal Fluorescein Staining

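### The SAP omits, without declaring it, the protocol's baseline-to-worst shift for ocular safety assessments, and no table counts measured acuity losses of 0.22 logMAR or more by arm

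*SAP*

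**What the plan says.** **Protocol.** The Safety Variables part of the synopsis states: "Other safety endpoints including visual acuity, slit-lamp biomicroscopy and intranasal endoscopic examination will be summarized by treatment group and visit using descriptive statistics". The same paragraph adds that "shifts from baseline to worst on-treatment value for ocular safety assessments will be summarized". Appendix 2, under the logMAR calculations, sets a threshold: "A clinically significant visual acuity decrease (defined as an increase of 0.22 or greater in logMAR score"). A loss of that size from screening "should be evaluated by the Investigator as a potential AE". Section 10.4.7 (Safety Variables) is redacted, so the commitment to a worst-value shift is visible only in the synopsis.

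**SAP.** Section 1 says that the SAP's methods take precedence over the protocol's. Section 15.2 says "The observed and change from baseline visual acuity will be summarized for each eye (study eye and fellow eye) using continuous descriptive statistics", by visit and arm, and adds a subject listing. Section 9.4 defines those statistics as n, mean, SD, median, minimum and maximum. Section 15.3 plans slit-lamp shift tables from baseline to post-treatment at Visit 1 and to post-CAE at Visit 2. The table list has one acuity table (14.3.2) and one slit-lamp shift table (14.3.3.2). Neither 15.2, 15.3 nor any table title mentions a worst value or the 0.22 threshold. Section 15.1 counts ocular treatment-emergent adverse events by arm, at subject and event level and by eye. Section 18 lists a revised EDS primary analysis, an added covariate and an added pupil-diameter analysis, and nothing on the worst-value shift.

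**The concern.** There are two gaps, and they differ in standing.

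The first is a departure from the protocol. A planned safety summary has gone from the governing document, and the section meant to record such changes is silent.

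The second is a gap in what the tables can show. Harm to vision, if it occurred, could take the form of a large loss in a few subjects, not a small loss in all. A reader comparing three doses with placebo would then want to know how many subjects in each arm lost a meaningful amount of vision. The protocol supplies the definition of meaningful, but no planned table applies it to the measurements. The only by-arm count passes through the investigator's decision on whether to record an adverse event.

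**Working it through.** **1. Commitment against plan**

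| Item | Protocol synopsis | Visible SAP |
|---|---|---|
| Acuity, by visit | descriptive statistics | yes (15.2, Table 14.3.2) |
| Acuity, baseline to worst | covered by the sentence on ocular assessments | absent |
| Slit lamp, by visit | descriptive statistics | yes, with shifts (15.3, Tables 14.3.3.1 and 14.3.3.2) |
| Slit lamp, baseline to worst | covered by the same sentence | absent |
| Change declared | not applicable | not in Section 18 |

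**2. The protocol's own figures**

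- Worked acuity example (Appendix 2): 0.1 + 4 × 0.02 = 0.18 logMAR. This reproduces.
- Threshold in letters, at 0.02 per letter: 0.22 / 0.02 = 11 letters.
- Completers (Section 10.3): 40 × (1 − 0.05) = 38 per arm. This reproduces.

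**3. What the planned statistics show when a few subjects lose vision**

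Suppose k of n = 40 subjects in an arm lose 0.30 logMAR (15 letters) and the rest are unchanged. The mean change is 0.30k/40. The SD is √[(k × 0.30² − 40 × mean²)/39].

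| k | Mean | Median | SD | Maximum | Count at 0.22 or more |
|---|---|---|---|---|---|
| 1 | 0.0075 | 0 | 0.047 | 0.30 | 1/40 = 2.5% |
| 2 | 0.015 | 0 | 0.066 | 0.30 | 2/40 = 5.0% |
| 4 | 0.030 | 0 | 0.091 | 0.30 | 4/40 = 10.0% |

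For k = 2 the SD is √[(0.18 − 0.009)/39] = 0.066. The mean shift of 0.015 is 0.75 of a letter. The maximum shows that at least one subject crossed the threshold, but it is the same in all three rows. The SD rises with k here only because everyone else is set to exactly zero. With ordinary measurement variation it could not be turned back into a count.

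Losses exactly at the threshold move the mean less: 0.22k/40 = 0.0055, 0.011 and 0.022 for k = 1, 2 and 4.

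**4. Can the mean reveal this?**

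The documents give no SD for logMAR change. Assume 0.05 to 0.10. The 95% half-width of a 40-subject mean is then 1.96 × SD/√40, from 0.015 to 0.031. A shift of 0.015 from two affected subjects is no larger than the smaller of these.

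**5. When would worst value and visit value differ?**

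They coincide for a subject whose only post-dose examination is the one at Visit 1. They can differ for a subject examined again at Visit 2, at an unscheduled visit (Protocol 8.4.2: "These visits may be performed in order to ensure subject safety") or at early termination, when participants "will be asked to complete safety assessments (if the participants agree) prior to study exit" (Protocol 4).

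How many have a Visit 2 examination is unclear. Protocol Appendix 1 and SAP 4.2, 15.2 and 15.3 leave post-CAE acuity and slit lamp to the investigator's discretion. Protocol 8.3.1 lists both at Visit 2 without that condition. These passages must be reconciled.

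**The case against.** Several stronger readings are tempting, and the documents do not support them.

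- **That acuity is reported only as means.** It is not. SD, median, minimum and maximum of the change are also given by eye, visit and arm, and the maximum flags any loss of 0.22 or more in the values summarized.
- **That such losses are never counted by arm.** Losses recorded as adverse events are counted in the ocular tables, and the listing permits a count by hand. What is missing is a prespecified count of measured losses that does not depend on the adverse-event judgement.
- **That the protocol promised a table at 0.22.** Appendix 2 uses the threshold only to prompt evaluation of a possible adverse event. The synopsis sentence on worst values names no threshold.
- **That unscheduled and early-termination examinations reach listings only.** The visible SAP assigns them to no summary, but SAP 9.2 on data handling is redacted and may contain a rule.

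It can also be said that the worst value adds little in a study with two single doses and at most two scheduled post-dose examinations, that the protocol side rests on the synopsis, and that the SAP is entitled to supersede the protocol. The first is fair and limits the size of the point. The second is true, but the synopsis sentence is explicit. The third gives the SAP authority to change a method, but a change still belongs in Section 18. Finally, a percentage that draws on a discretionary Visit 2 examination depends on who was examined. That stands, and the fix must deal with it.

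**Conclusion.** The point holds in limited form. The visible SAP omits the baseline-to-worst shift for acuity and slit lamp and does not declare the change. Separately, no table gives a by-arm count of measured losses of 0.22 logMAR or more that is independent of the adverse-event judgement. The planned statistics cannot stand in for that count: in the illustration the median stays at zero and the maximum stays at 0.30 whether 2.5% or 10% of an arm is affected.

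This is a minor-to-moderate issue of safety reporting, and no efficacy conclusion depends on it. The illustration assumes losses of 0.30 in a few subjects and none elsewhere. The precision range assumes an SD of 0.05 to 0.10, which is not in the documents. The conclusion also assumes that the redacted text, notably Protocol 10.4.7 and SAP 9.2, neither withdraws the commitment nor supplies the missing summary.

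**What to change.** - **SAP 15.2 and Table 14.3.2:** add the worst post-dose change, and n (%) per arm and eye with a logMAR increase of 0.22 or more from screening.
- **SAP 15.3 and Table 14.3.3.2:** add the shift from baseline to the worst post-dose grade.
- **Definition of worst:** state that any post-dose examination counts, including unscheduled and early-termination ones, unless SAP 9.2 already sets a rule.
- **Denominator:** treated subjects with at least one post-dose value. Show the number examined at Visit 2 by arm.
- **Visit 2 examinations:** reconcile Protocol 8.3.1 with Protocol Appendix 1 and SAP 4.2, 15.2 and 15.3.
- **If the worst-value shift is not restored:** record and justify its removal in Section 18.

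The cost is SAP wording and a few table rows from data already planned for collection. The small downside, besides programming, is that the Visit 2 contribution depends on who was examined. The Visit 2 numbers by arm make that visible.
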